9.11.2.1. Analysis of Primary Outcome

Prevalence of the primary outcome will be calculated according to the conventions described in [Table 9.6](#). In general, prevalence will be calculated by dividing the number of cases with an MCM by the appropriate denominator. Prevalence is preferred over incidence when examining pregnancy outcomes, such as congenital malformations, because incidence cannot be reliably estimated given the complexities in the reproductive process.⁹⁷

For MCM, prevalence in the exposed cohort will be calculated among the subset of individuals who are exposed during the first trimester. For the primary analysis, prevalence will be calculated among live births, and a secondary analysis will be conducted among live births and fetal losses ([Table 9.6](#)).

The unweighted univariate regression will be used to compare the crude (unadjusted) relative risks (RRs) of MCM in the tirzepatide exposed and each of the comparator groups, respectively: tirzepatide exposed vs. AOM active comparator and tirzepatide exposed vs. AOM unexposed comparator.

Adjusted methods will incorporate weights estimated using the inverse probability of treatment weighting (IPTW) method to balance the cohorts regarding observable covariates. A weighted generalized linear model using a binomial family and a log (RR) link with robust sandwich variance estimation or a modified Poisson regression⁹⁸ with robust error variance will be employed to estimate an adjusted RR. As with the unweighted analysis, two sets of comparisons will be conducted separately: tirzepatide vs. AOM active comparator and tirzepatide vs. AOM unexposed comparator.

The adjusted comparison of the overall prevalence of MCM observed in the tirzepatide exposed and the comparator cohorts will be considered the primary analysis. A p-value <0.05 will be considered statistically significant.

Table 9.6. Calculation of Primary Outcome Prevalence

Outcome	Numerator	Denominator
Primary analysis: among live births	Live births with confirmed (by adjudication) MCMs (excluding MCMs not known to be associated with medication exposure ^a) among individuals with pregnancy outcome data and, if applicable, exposure during 1 st trimester	Live births among individuals with pregnancy outcome data and, if applicable, ^b exposure during 1 st trimester
Secondary analysis: among all pregnancy outcomes	Live births and fetal losses ^c with confirmed (by adjudication) MCMs (excluding MCMs not known to be associated with medication exposure ^a) among individuals with pregnancy outcome data and, if applicable, exposure during 1 st trimester	Live births and fetal losses ^c among individuals with pregnancy outcome data and, if applicable, exposure during 1 st trimester

Abbreviation: MCM = major congenital malformation.

^a To avoid misattribution of the malformation to the medication, MCMs not known to be associated with medication exposure such as chromosomal abnormalities, genetic syndromes, fetal alcohol syndrome, prematurity-related conditions in infants born at <36 gestational weeks (e.g., patent ductus arteriosus, patent foramen ovale, inguinal hernias, or undescended testes), and positional effects (e.g., hip dislocation due to breech position or abnormal skull shape due to crowding by multiple fetuses) will not be considered MCMs in the statistical analyses comparing MCM prevalence between the cohorts.⁵¹

^b Exposure during first trimester applicable only for exposed cohorts.

^c Fetal losses include stillbirths, SABs, and induced abortions.

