There are limited data on the safety of tirzepatide use during pregnancy. Available data are insufficient to identify a potential drug-associated risk of major birth defects, spontaneous abortion, or other adverse maternal or fetal outcomes.

This study is an observational post-authorization safety study (PASS) and is a post-marketing requirement for regulatory authorities.

Research question and objectives

The aim of the Tirzepatide Pregnancy Registry study is to compare the maternal, fetal, and infant outcomes of individuals treated with tirzepatide for weight management during pregnancy (tirzepatide exposed cohort) with outcomes in two comparator cohorts:

- Anti-obesity medication [AOM] active comparator cohort: Individuals who are treated with pharmacotherapy other than tirzepatide or other therapies with GLP-1 receptor agonist (GLP-1 RA) activity for weight management during pregnancy.
- AOM unexposed comparator cohort: Individuals who have obesity or are overweight with at least one weight-related comorbid condition at the time of conception; and who are not treated with tirzepatide, GLP-1 RA therapies, or any other approved products for weight management during pregnancy.

The primary objective is to describe and compare the overall prevalence of major congenital malformations (MCM) among individuals treated with tirzepatide during pregnancy for weight management relative to each of the two comparator cohorts of pregnant individuals (AOM active comparator cohort and AOM unexposed comparator cohort).

The secondary objective is to describe and compare the prevalence of maternal pregnancy complications, fetal and infant outcomes other than MCM, and postnatal growth and development outcomes between pregnant individuals treated with tirzepatide during pregnancy

for weight management and the two comparator cohorts of pregnant individuals (AOM active comparator cohort and AOM unexposed comparator cohort). The secondary outcomes of interest are as follows:

- Maternal pregnancy complications (gestational diabetes, pregnancy-induced hypertension, pre-eclampsia, eclampsia)
- Fetal outcomes (spontaneous abortion, induced abortion, stillbirths)
- Infant outcomes (minor congenital malformation, preterm birth, small-for-gestational age)
- Postnatal growth and development outcomes (postnatal growth deficiency up to one year of age, infant developmental delay up to one year of age)

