7.3.2. Clinical Trial Data

A Phase 1 study of tirzepatide in healthy lactating females (NCT05978713) has shown that following a single 5-mg dose, the concentration of tirzepatide in breastmilk was found to be undetectable to very low compared to plasma concentrations. Because tirzepatide is an amino acid sequence, any low amount present in breastmilk is expected to be degraded and not orally absorbed as intact drug by the breastfed infant.² On the other hand, there are currently no clinical data available for exposure to tirzepatide given subcutaneously during pregnancy. Clinical trials that assessed the efficacy of tirzepatide for the treatment of obesity among adults excluded pregnant individuals, and use of contraception was required for individuals of child-bearing potential during the study.³⁻⁶ Therefore, the potential risk of tirzepatide treatment during pregnancy remains unknown.

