9.7.3. Outcome Definitions and Ascertainment

Table 9.3 presents the definitions of the outcomes. For outcomes not simply reported by the HCP, additional information on outcome ascertainment is provided.

Table 9.3. Definitions of Outcomes

Outcome	Clinical Definition	Operational definition
Major congenital malformation (MCM)	An abnormality of body structure or function that is present at birth; is of prenatal origin (i.e., birth defect); has significant medical, social, or cosmetic consequences for the affected individual; and typically requires medical intervention ⁴⁸	
The registry defines and codes MCMs with criteria specified by the CDC MACDP (Annex 3).⁴⁹ When participants who reside in Europe are enrolled, MCMs will also be defined and coded using the criteria specified by the EUROCAT⁵⁰ (Annex 3).
 
Exclusion criteria for MCM analyses include exposure to known teratogens and/or investigational medications, and/or congenital infectious agents (e.g. zika, TORCH, HIV). To avoid misattribution of the malformation to the medication, MCMs not known to be associated with medication exposure, such as chromosomal abnormalities, genetic syndromes, fetal alcohol syndrome, prematurity-related conditions in infants born at <36 gestational weeks (e.g., patent ductus arteriosus, patent foramen ovale, inguinal hernias, or undescended testes), and positional effects (e.g., hip dislocation due to breech position or abnormal skull shape due to crowding by multiple fetuses), will not be considered MCMs in the statistical analyses.⁵¹
 
Adjudication process: A panel of 2–3 independent experts in clinical genetics and neonatology, blinded to exposure, will review all malformations reported to the registry among live and non-live births and classify them using the CDC's MACDP system for US-reported cases (and EUROCAT, for EU-reported cases). Additionally, the birth defect evaluators will provide the organ system involved, etiology of the defect (e.g., chromosomal abnormality, prematurity), and approximate timing of the development of observed defects. If additional information is needed to aid in classification, the birth defect evaluators will request additional information using the targeted follow-up process outlined in Section 9.6.2. These assessments will be recorded in the study database. If there is a discrepancy, a third expert will independently review and code the case serving as tie breaker. These reviews will occur soon after the malformation is reported. Additional reviews will occur if new information is received for the case. The SAC that will not be blinded to exposure will assess the possible temporal association between exposure (to tirzepatide) and the development of observed defects. Additionally, the SAC will review all malformation cases reported to the registry and reach consensus on the coding of each case. The sponsor will not be involved in any activities related to case review or adjudication.

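### The exclusion rule in the primary MCM numerator is mis-stated and open-ended: its general phrase does not match its own examples and leaves malformations of unknown cause unprotected

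*Protocol*

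**What the plan says.** Protocol section 9.11.2.1, Table 9.6, defines the primary numerator as "Live births with confirmed (by adjudication) MCMs (excluding MCMs not known to be associated with medication exposure", with footnote a attached. The secondary row, which covers live births and fetal losses, carries the same exclusion.

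Footnote a opens with its purpose, "To avoid misattribution of the malformation to the medication", and then describes what is left out: "MCMs not known to be associated with medication exposure such as chromosomal abnormalities, genetic syndromes, fetal alcohol syndrome, prematurity-related conditions" in infants born before 36 weeks, and positional effects. It applies the exclusion to the statistical comparison of MCM prevalence between cohorts. Table 9.3 in section 9.7.3 uses the same phrase with the same examples: "MCMs not known to be associated with medication exposure, such as chromosomal abnormalities, genetic syndromes, fetal alcohol syndrome".

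Table 9.3 also describes adjudication. A panel blinded to exposure classifies every reported malformation and records, among other things, the "etiology of the defect (e.g., chromosomal abnormality, prematurity"). The SAC, which the same entry says is not blinded to exposure, then reviews all malformation cases and reaches consensus on the coding of each. Section 9.20 likewise gives the SAC the task of reviewing and classifying reported MCMs.

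On current knowledge, the abstract says "Available data are insufficient to identify a potential drug-associated risk of major birth defects", and section 7.3.2 says "the potential risk of tirzepatide treatment during pregnancy remains unknown".

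**The concern.** There are two possible rules, and the text mixes them.

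- **Rule implied by the examples:** exclude an MCM when a cause other than medication has been established.
- **Rule in the general phrase:** exclude an MCM unless its link to medication is already known.

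The two agree on chromosomal, genetic, alcohol-related, prematurity-related and positional cases. They disagree on a structural malformation of unknown cause whose type has no recognised drug link. The first rule counts it and the second removes it. A new drug-related pattern would fall in that group, and the protocol says that no tirzepatide-associated risk can yet be identified.

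The rule defines the primary endpoint of a safety registry. Because the list is only illustrative, the general phrase governs any case that is not listed, and the decision to exclude is made after the outcome is known. A committee aware of exposure takes part in the coding. A closed list would limit that discretion; the present wording does not.

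**Working it through.** **1. The passages side by side**

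| Type of MCM | General phrase | Rule implied by the examples |
|---|---|---|
| Chromosomal, genetic, fetal alcohol, prematurity-related before 36 weeks, positional | Excluded | Excluded |
| Unknown cause, type already linked to some medication | Counted | Counted |
| Unknown cause, type with no recognised drug link | Excluded | Counted |

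The third row is the whole difference. Table 9.3 has etiology recorded, but no sentence there or in Table 9.6 says how an MCM of unknown etiology is counted.

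**2. Would another planned analysis show the loss?** No. The secondary MCM analysis in Table 9.6 applies the same exclusion. The supplementary analyses (9.11.2.6) bring back excluded participants, and the sensitivity analyses (9.11.2.7) vary enrolment definition, weighting, exposure window and similar choices. Neither brings back excluded malformations.

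**3. The plan's own sample size.** Inputs from section 9.9.1: comparator prevalence p1 = 0.03; relative risk 3, so p2 = 0.09; two-sided alpha 0.05; power 80%; 1:1 allocation; Fisher's exact test with the Walters approximation. The formula is

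power = Φ( √(2n) · [arcsin√(p2 − 1/(2n)) − arcsin√(p1 + 1/(2n))] − 1.96 ).

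With n = 265: arcsin√0.08811 = 0.3014 and arcsin√0.03189 = 0.1795, a difference of 0.1218. Then √530 × 0.1218 = 2.805, and Φ(2.805 − 1.96) = 0.801. With n = 264 the power is 0.799, so 265 is the smallest n that reaches 80%. Enrolment is 265/0.9/0.9/0.9 = 363.5, rounded up to 364. Both stated figures reproduce. Full enumeration of Fisher's exact test at 265 per cohort gives 80.7%.

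**4. Hypothetical size under the literal reading.** The documents do not say what share of MCMs would be removed, so the shares below are assumptions that only show scale.

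(a) The same share is removed in both cohorts. The relative risk stays at 3 and only the event rate falls.

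| Share removed | Prevalences compared | Power at 265, Walters | Power at 265, exact Fisher |
|---|---|---|---|
| 0% | 3.0% vs 9.0% | 80% | 81% |
| 20% | 2.4% vs 7.2% | 69% | 69% |
| 40% | 1.8% vs 5.4% | 53% | 54% |
| 60% | 1.2% vs 3.6% | 34% | 33% |

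(b) Only part of the 6-point excess (9% − 3%) is removed, because its pattern is new. The comparator's 3% is left whole.

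| Share of excess removed | Prevalence in exposed | Observed relative risk | Power at 265, Walters | Power at 265, exact Fisher |
|---|---|---|---|---|
| 25% | 7.5% | 2.5 | 58% | 59% |
| 50% | 6.0% | 2.0 | 31% | 32% |

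The scenarios answer different questions. In (a) power falls without bias in the ratio; in (b) the ratio is pulled toward 1.

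**The case against.** The strongest reply is that nobody would apply the phrase literally. Footnote a gives the purpose, every example has an established non-drug cause, and the sentence cites a published set of inclusion and exclusion criteria for malformations. The natural repair is a misplaced negation: known not to be associated. The objective and the sizing concern overall MCM prevalence, all malformations are collected and reviewed, and the exclusion is confined to the cohort comparison, so a new pattern would still be seen by the panel and the SAC. Most of this stands. It makes the conventional exclusion the probable intent. It does not settle the rule, because the list remains illustrative and unknown etiology is not addressed.

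A reader might go further and infer that the plan drops all malformations of unknown cause, including any tirzepatide-specific defect, and is therefore underpowered or biased toward no effect. The documents do not support that. The phrase speaks of medication in general, so a type already linked to any drug stays in even when the cause in that case is unknown. The removed shares are not documented. Scenario (a) does not bias the ratio, and scenario (b) does so only by assuming that background cases are untouched, which the literal rule would not guarantee. Part of any fall in event rate would also remain after rewording, because the intended exclusions remain.

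It is also fair to say that adjudication always follows the outcome and that the panel recording etiology is blinded. That limits differential exclusion at the panel step. It does not cover the later SAC consensus.

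Finally, handling of unknown etiology might be left to the SAP or an adjudication charter, neither of which is at hand. But the protocol already fixes the rule. A later document would either carry the phrase forward or depart from it.

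**Conclusion.** The point holds as a mis-stated, open-ended rule in the definition of the primary endpoint. The general phrase and its examples set different tests; they part on malformations of unknown cause with no recognised drug link, and no planned analysis would show the effect of excluding these. The room for case-by-case exclusion matters more because the SAC is not blinded to exposure. The documents do not say that the SAC may overrule the panel on exclusions, so this is an opening and not evidence of bias.

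No loss of cases is demonstrated and no stated figure is wrong: 265 and 364 reproduce and stand. The power figures under the literal reading rest on assumed shares and should be quoted only as hypothetical. The change is worth making because the rule governs the primary result and the repair is nearly free.

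**What to change.** In Table 9.3, both rows of Table 9.6 and footnote a, replace the general phrase and the illustrative list with a closed rule, for example:

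> Excluded are MCMs for which the blinded panel documents an established cause other than medication exposure, limited to: chromosomal abnormality; genetic syndrome; fetal alcohol syndrome; the listed prematurity-related conditions at <36 weeks; the listed positional effects. MCMs of unknown etiology are counted.

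Add one sensitivity analysis that counts all adjudicated MCMs, including the excluded categories, so that the effect of the exclusion can be seen.

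The cost is wording in two tables and a footnote, plus one extra analysis run. No new data are needed, since the panel already records etiology, and the sample size does not change.

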It is possible that outcomes among pregnant individuals and infants lost to follow-up could differ from those with documented outcomes. Because of differences in individual reporting patterns, it is currently not possible to assess with any certainty what impact the potential biases from the losses to follow-up may have on the analyses. However, the characteristics of those participants considered lost to follow-up will be descriptively compared with those in the main analysis population to address this potential source of bias.

Pregnancies that result in fetal losses (stillbirths, SABs, and induced abortions) without reported MCMs may introduce a classification bias. The percentage of these pregnancies consisting of potentially normal outcomes or MCMs is unknown. The data collection form attempts to obtain information on MCMs detected at the time of the outcome. However, the reporting HCP may not know the condition of the lost fetus. Additionally, recent changes in legislation around abortion within the US may lead to underreporting and/or misclassification of outcomes due to both patient and HCP concerns around legal repercussions of reporting.

Each source of potential bias will be evaluated descriptively and discussed in the report.

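### The secondary MCM analysis in Table 9.6 counts fetal losses of unknown malformation status as non-cases, which can bias its relative risk when loss shares differ between cohorts

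*Protocol*

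**What the plan says.** Section 9.11.2.1 sets out two MCM analyses: "For the primary analysis, prevalence will be calculated among live births, and a secondary analysis will be conducted among live births and fetal losses". In Table 9.6 the secondary numerator is "Live births and fetal losses ^c with confirmed (by adjudication) MCMs", after removal of malformations not known to be related to medication, such as chromosomal abnormalities. The denominator is "Live births and fetal losses ^c among individuals with pregnancy outcome data and, if applicable, exposure during 1 st trimester". The footnote reads "Fetal losses include stillbirths, SABs, and induced abortions". The table sets no gestational-age limit and does not require that the fetus was examined.

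Section 9.13 recognises the difficulty: "Pregnancies that result in fetal losses (stillbirths, SABs, and induced abortions) without reported MCMs may introduce a classification bias". It adds that the share of such losses with and without MCMs is not known. It also says: "However, the reporting HCP may not know the condition of the lost fetus". The response there is descriptive evaluation and discussion in the report.

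Relevant data are collected. Section 9.8 lists prenatal test results, post-mortem findings for losses and the reason for an induced abortion. Table 9.3 extends adjudication to non-live births.

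**The concern.** The two halves of the Table 9.6 fraction follow different rules. Numerator entry needs positive evidence of an MCM. Denominator entry needs only a known pregnancy outcome. A loss with no information about malformation therefore counts in the same way as one examined and found normal, although Section 9.13 treats the first kind as unknown.

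This matters because it is the only specified MCM analysis that includes losses, so it is what a reader would set beside the live-birth primary result to judge whether affected pregnancies were lost before birth. The share of losses is also not neutral: spontaneous abortion, induced abortion and stillbirth are secondary outcomes that exposure might change. Section 9.13 describes left truncation as well, so a difference in enrolment timing alone could make the loss shares differ.

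Elsewhere the protocol applies the stricter rule. In Table 9.7 the sensitivity denominators for small for gestational age, postnatal growth deficiency and developmental delay require the relevant measurement. No equivalent exists for MCM in losses.

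**Working it through.** **Inputs**
- Comparator loss share L0 = 10%, the complement of the 90% live-birth assumption in Section 9.9.1.
- Live-birth MCM prevalence p = 3% in the comparator, and a target RR of 3 (9% in the exposed cohort), Section 9.9.1.
- Exposed loss share L1 = 20% or 30%. These are assumptions; the protocol gives no figure.
- q, the recorded MCM share among losses. The protocol gives no figure; the range used is 0 to 10%.
- The true RR is taken to be the same in losses as in live births.

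**The plan's own figure.** Fisher's exact test with the Walters approximation, two-sided 5% and 1:1, gives 265 live births per cohort with 80.1% power for 3% vs 9%. Then 265/0.9³ = 363.5, rounded up to 364, and 3 × 364 = 1,092. The protocol's figures are reproduced. It states none for the secondary MCM analysis.

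**Formula.** Recorded secondary prevalence = (1 − L)·p + L·q.

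**Absolute prevalence at L = 10%, p = 3%**
- q = 0: 0.9 × 3% = 2.7%, a 10% relative dilution and the largest possible.
- q = 1.5%: 2.7% + 0.15% = 2.85%.
- q = 3%: 3.0%, no dilution.
- q = 10%: 2.7% + 1.0% = 3.7%, higher than in live births.

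**RR with no MCM recorded in losses (q = 0).** The RR is multiplied by (1 − L1)/(1 − L0).

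| L1 (L0 = 10%) | Factor | True 3.0 reads | True 1.0 reads |
|---|---|---|---|
| 10% | 0.90/0.90 = 1.000 | 3.00 | 1.00 |
| 20% | 0.80/0.90 = 0.889 | 2.67 | 0.89 |
| 30% | 0.70/0.90 = 0.778 | 2.33 | 0.78 |

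**Partial detection.** Let a fraction d of the MCMs in losses be recorded, the same in both cohorts. At L1 = 20% and true RR 3.0:
- d = 25%: (0.8 × 9% + 0.2 × 2.25%)/(0.9 × 3% + 0.1 × 0.75%) = 7.65%/2.775% = 2.76.
- d = 50%: 8.10%/2.85% = 2.84.

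**Equal loss shares.** With L1 = L0 and the same d, numerator and denominator of the RR shrink by the same factor, and 3.0 stays 3.0.

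**Upward bias.** Take a live-birth RR of 1, L1 = 20%, and losses carrying a higher recorded MCM share than live births, for example through terminations after a prenatal finding:
- q = 5%: (2.4% + 1.0%)/(2.7% + 0.5%) = 3.4%/3.2% = 1.06.
- q = 10%: (2.4% + 2.0%)/(2.7% + 1.0%) = 4.4%/3.7% = 1.19.

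**Power.** The secondary analysis has about 265/0.9 = 294 pregnancies per cohort. By the same Walters method with q = 0, power is about 80% with equal losses (2.7% vs 8.1%) and about 66% with L1 = 20% (2.7% vs 7.2%).

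**The case against.** The case for leaving Table 9.6 alone has real weight.

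- **The direction is not fixed.** A reader might infer that the rule always makes a drug that raises early loss look safer. The documents do not support that. Confirmed MCMs in losses enter the numerator, and a high recorded share among losses raises the RR. This stands.
- **The documents do not say that status is mostly unobservable.** Section 9.13 says only that it may be unknown. It is fair to note that Table 9.3 puts spontaneous abortion before 20 weeks, while the section on prospective enrolment places the structural scan at about 20 weeks. That makes missing status plausible for many such losses, but it gives no proportion.
- **The size is modest.** A reader could take the reference rates in Table 9.4 (spontaneous abortion 11.8%, stillbirth about 0.6%, 18.6 induced abortions per 100 live births), obtain a live-birth share of (1 − 0.118 − 0.006)/1.186 = 0.739, and so infer 26% dilution. Those are general-population rates. The plan's registry assumption is 90% live births, and late enrolment removes people who have already had a loss. The 10% figure is the one to use.
- **A large rise in losses would be seen directly.** Losses are compared in their own right. For a 10% base rate, Table 9.4 (small-for-gestational-age row) needs 215 per cohort for RR 2 and 70 for RR 3, against about 364 × 0.9 = 328 after exclusions. This limits the harm, but it does not correct the MCM estimate.
- **Section 9.11.2.7 promises sensitivity analyses for missing data.** These do not reach the problem as written, because Table 9.6 makes these losses non-cases and leaves nothing to be treated as missing. None of the other listed sensitivity analyses changes the MCM denominator.

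The bias is also disclosed, and the live-birth primary analysis is untouched.

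**Conclusion.** The point holds in a conditional form. Table 9.6 scores losses of unknown malformation status as unaffected, in conflict with what Section 9.13 says is known about them. The secondary RR can be biased in either direction when loss shares differ between cohorts. With no MCM recorded in losses, a 10% comparator share and an assumed 20% in the exposed cohort, 3.0 reads 2.67 and 1.0 reads 0.89. Partial detection shrinks the effect. The exposed loss shares and the detection rates are assumptions, so these figures illustrate size and do not forecast it. The issue is confined to a secondary analysis, but that analysis is the complement to the live-birth result, and the remedy uses data already collected.

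**What to change.** Amend Table 9.6 as follows.

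1. Classify each fetal loss as MCM, no MCM (status documented by prenatal imaging, pathology or post-mortem) or unknown, and report the three counts by cohort.
2. Keep the all-losses analysis as now defined.
3. Add a version limited to live births plus losses with documented status.
4. Add bounding RRs that treat unknown-status losses as unknown, over a prespecified range for the MCM share among them.

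Do not restrict the analysis to losses at 20 weeks or later. That would remove earlier terminations with a confirmed MCM, which are among the cases a live-birth analysis misses.

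The cost is protocol wording, one extra table and a wider stated range. The range in item 4 matters: if all losses were unknown at 10% in both cohorts and the live-birth RR were 1, extreme bounds (none affected in one cohort, all in the other) would run from 2.7%/12.7% = 0.21 to 12.7%/2.7% = 4.70, too wide to inform. Losses with documented status may also be enriched for MCM, so the documented-status version should be read with the all-losses version as a pair of bounds, not as a corrected estimate.
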